### 5.1.2.8 Dose-limiting toxicity (DLT)

Dose-limiting toxicity (DLT) will be defined as the occurrence of any of the **treatment-related** toxicities occurring up to and including Study Day 28, which are listed in [Table 5-3](#), using the Common Terminology Criteria for Adverse Events (CTCAE) v4.03.

For the purpose of dose-escalation decisions, only DLTs will be necessarily considered and included in the BLRM. However, adverse events, which occur after Study Day 28 and meet all the criteria for the DLT definition apart from the timing of occurrence, will be considered in ultimate decisions of dose escalation and determinations of how many patients should be evaluated at a given dose level. Prior to enrolling patients into a higher dose level, all adverse events will be reviewed for all patients at the current and the previous dose levels.

For toxicities which, by definition, require a time-window for them to be defined as DLTs (grade 3 non-hematologic toxicity for  $\geq 7$  consecutive days), a subsequent visit(s) and/or laboratory assessment(s) must be scheduled accordingly, in order for this toxicity to qualify as a DLT. For example, if a grade 3 non-hematologic toxicity is observed, it must be also observed at least 7 days later, with no intervening lower grades, in order to qualify as a DLT.

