**\* At the discretion of the Investigator, laboratory values can be confirmed with a second assessment. In this case, only the result of the second assessment will be considered valid and final.**

Adverse events occurring after Study Day 28 will not be considered DLTs, however, they may be considered in further decisions regarding the number of patients to enroll in a given dosing cohort. If a patient is not followed for the 28-day period following Study Day 1 due to discontinuation, for reasons other than DLTs, or if, from Study Day 1 through Study Day 28, a patient misses  $> 6$  consecutive doses of treatment or  $> 20\%$  of the planned study drug doses, another patient will be enrolled into that dose level and stratum. For toxicities which, by definition, require a time-window for them to be defined as DLTs (grade 3 non-hematologic toxicity for  $\geq$  7 consecutive days) a subsequent visit(s) and/or laboratory assessment(s) must be scheduled accordingly, in order for this toxicity to qualify as a DLT. A minimum of 9 evaluable patients from each stratum (stratum 1 consists of patients with baseline PLT counts  $75-99 \times 10^9/L$  and stratum 2 consists of patients with baseline PLT counts  $50-74 \times 10^9/L$ ) must be treated at the dose declared to be the MSSD.

Enrollment of patients and dose escalation will be performed as described in [Section 5.1.2.1](#), [Section 5.1.2.2](#), [Section 5.1.2.3](#) and [Section 5.1.2.4](#).

Intra-patient escalation during the dose escalation phase of the study will be allowed according to the rules described in the [Section 5.1.2.6](#).

[figure not shown]
Following determination of the MSSD, a safety expansion phase will be conducted. Patients from both strata can be enrolled simultaneously during the safety expansion phase, allocated to a dose equal to the respective MSSD for their stratum. If the MSSD is the same in both strata, all patients in the safety expansion phase will be treated with the same dose, regardless of the baseline PLT counts.

In the safety expansion phase, the safety and tolerability of the MSSD will be further evaluated with the purpose of establishing that this dose is suitable for use in the low-platelet population of patients with MF. The Bayesian logistic regression model (BLRM) with escalation with overdose control (EWOC) will continue to be updated with data from patients participating in the safety expansion phase.

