#### **5.1.2.5 Safety expansion phase**

Once the MSSD of INC424 is identified for both strata in the dose escalation phase of this study, additional patients will be enrolled and treated at this dose in order to further evaluate its safety and tolerability and to obtain estimates of efficacy, with the purpose of establishing that this dose is suitable for use in the low-platelet population of patients with MF. Patients from both strata can be enrolled simultaneously during the safety expansion phase. If the MSSD is identical in both strata, all patients in the safety expansion phase will be treated with the same dose. Prior to Amendment 4, twenty patients (10 patients from each stratum), in addition to the patients treated at the MSSD during the dose escalation phase, were to be evaluated during this part of the study. If the MSSD proves not to be well tolerated with further experience and via continuous update of the Bayesian logistic regression model during this safety expansion phase, then a lower dose may be evaluated to twenty additional patients (10 patients from each stratum).

With the approval of Amendment 4, all new patients enrolled to Stratum 1's safety expansion phase will be given the 10 mg BID dose, instead of the 15 mg BID dose level previously evaluated as the MSSD. This will allow 10 mg BID to be evaluated as the starting dose. Approximately 20 patients will be evaluated at this dose level in Stratum 1, inclusive of the patients already enrolled into this dose during the dose escalation phase, OR the Last Patient's First Visit (LPFV) will occur on 01 September 2017, whichever comes first. Patients already taking the 15 mg BID dose in Stratum 1's safety expansion phase will continue to take their assigned dose. Stratum 2 will maintain its original enrollment requirement of 10 patients at the MSSD.

The criteria for continuation of treatment and dose modification guidelines employed during the dose escalation phase will also be followed during safety expansion phase. Dose escalation above the MSSD will not be allowed.

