**Table 5-4 Criteria for interruption and re-initiation of INC424 treatment – Recommended dose modifications**

Worst Toxicity (CTCAE Grade unless otherwise specified)	Study Day 1 through Study Day 28		Study Day 29 to End of Treatment (EOT)
	Treatment related toxicity	Non-treatment related toxicity	
	Causality of toxicity and relation to the treatment with INC424 is based on the Investigator's expert judgment		
Hematological			
Neutropenia			
Grade 1	Continue at same dose level	Continue at same dose level	Continue at same dose level
Grade 2	Continue at same dose level	Continue at same dose level	Continue at same dose level
Grade 3	Continue at same dose level	Continue at same dose level	Continue at same dose level
Grade 4	
*Hold dosing
 
* qualifies as a DLT
	
Hold dosing
	
Hold dosing

	
In case of grade 4 neutropenia, follow-up rules according to Section 5.1.2.9.1. For dose restart guidelines, see Table 5-6.
		
Grade $\geq 3$ febrile neutropenia (ANC $<1.0 \times 10^9/L$ , isolated fever $\geq 38.3^\circ C$ or sustained fever $>38^\circ C$ for more than 1 hour)	
* Hold dosing until resolved to afebrile neutropenia <math>\leq</math> grade 2, then <math>\downarrow</math> 1 dose level**†
 
* qualifies as a DLT
 
** Resume therapy according to the rules of Section 5.1.2.7.
 
† If 2nd episode, then discontinue
	
Hold dosing until resolved to afebrile neutropenia <math>\leq</math> grade 2, then continue at same dose level‡
	
Hold dosing until resolved to afebrile neutropenia <math>\leq</math> grade 2, and:
 
if not related to INC424, then continue at same dose level***
 
if related to INC424, then <math>\downarrow</math> 1 dose level***
 
*** If a second episode of grade <math>\geq 3</math> febrile neutropenia occurs within 28 days, whether related or unrelated, the patient must discontinue

Worst Toxicity (CTCAE Grade unless otherwise specified)	Study Day 1 through Study Day 28		Study Day 29 to End of Treatment (EOT)
	Treatment related toxicity	Non-treatment related toxicity	
	Causality of toxicity and relation to the treatment with INC424 is based on the Investigator's expert judgment		
Hemorrhagic event of any kind			

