#### **6.1.3 Treatment period**

The core study period will consist of 2 phases: (a) the dose escalation phase and (b) the safety expansion phase that will start once the MSSD is determined. For each individual patient, the treatment period will begin on Study Day 1 and continue until Week 156. See [Table 6-1](#), [Table 6-2](#), and [Table 6-3](#) for more details.

With the implementation of Amendment 4, during the core treatment period, from screening until Day 168, on-treatment study visits are scheduled every 2 weeks in the first 8 weeks (Study Days 1, 15, 29, and 43), then every 4 weeks until Day 168 (Study Days 57, 85, 113,

141, and 168). Thereafter, in the extension study period, the on-treatment study visits will be every 12 weeks from Day 168 (on Days 252, 336, 420, 504, 588, etc.) through Week 144 and an EOT visit scheduled for Week 156. There will not be any required laboratory-only visits.

[The above paragraph will read as follows for the United Kingdom only:

For UK patients only, with the implementation of Amendment 4, during the core treatment period, from screening until Day 168, on-treatment study visits are scheduled every 2 weeks in the first 8 weeks (Study Days 1, 15, 29, and 43), then every 4 weeks until Day 168 (Study Days 57, 85, 113, 141, and 168). Thereafter, in the extension study period, the on-treatment study visits will be every 12 weeks from Day 168 (on Days 252, 336, 420, 504, 588, etc.) through Week 156. After Week 156, patients will return to the site every 12 weeks until LPFV plus 156 weeks, when the EOT visit will be performed. There will not be any required laboratory-only visits.]

For all patients, core treatment period visit windows are as follows: Day 15 has a  $\pm$  1-day window, Day 29 has a +3 day window, Day 43 has a  $\pm$  2-days window, Study Days 57, 85, 113, 141, and 168 have a  $\pm$  3-days window. Extension study period visits have a  $\pm$  7-day visit window.

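### After Amendment 4 no scheduled blood draw falls in the last 12-14 days of the 28-day DLT window, and no rule says how a laboratory DLT first seen on Days 29-32 is counted

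*Protocol*

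**What the plan says.** Protocol 5.1.2.8 counts as DLTs the listed treatment-related "toxicities occurring up to and including Study Day 28". Section 3.1 adds: "Adverse events occurring after Study Day 28 will not be considered DLTs". Three criteria in Table 5-3 are met through a blood result: platelets below 25 x10^9/L, ANC below 0.5 x10^9/L, and grade 2 or higher bilirubin with direct bilirubin of at least 0.5 mg/dL.

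Protocol 6.1.3, as amended, has core visits "scheduled every 2 weeks in the first 8 weeks (Study Days 1, 15, 29, and 43"). Day 15 may move one day either way, while "Day 29 has a +3 day window", so that visit cannot be brought forward. "There will not be any required laboratory-only visits". Table 6-1 puts both hematology and chemistry on Days 1, 15 and 29.

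Table 5-4 handles findings in the column "Study Day 29 to End of Treatment (EOT") separately. In that column a platelet count below 25 leads to a hold, or to discontinuation at 5 mg once daily, and carries no DLT label.

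The model stays live in expansion. Section 3.1 says it "will continue to be updated with data from patients participating in the safety expansion phase". Section 5.1.2.5 allows a lower dose to be tried if the MSSD proves poorly tolerated with further experience and "via continuous update of the Bayesian logistic regression model during this safety expansion phase". SAP 2.3.1 puts a table of posterior DLT probabilities in the study report, and SAP 2.3.2 summarises DLTs within the first 28 days.

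**The concern.** The primary endpoint is the DLT rate over 28 days, and thrombocytopenia was the DLT in the earlier phase I/II study. For patients starting under Amendment 4, a platelet, neutrophil or bilirubin value can cross its threshold after the Day 15 draw and not be measured until the window has closed. The documents do not say whether such a result belongs to the window. If it is left out, any error runs one way, towards fewer DLTs. The patients concerned are mainly the 10 mg BID expansion patients in Stratum 1, the group enrolled to evaluate that starting dose.

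Amendment 4 also cut the visit frequency and removed laboratory-only visits. These patients are therefore observed less densely than those treated earlier, including the 15 mg BID patients, and their DLT rates are not like for like.

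**Working it through.** **1. Unsampled part of the window.** Days left = 28 minus the day of the last scheduled draw.

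| Day 15 visit held on | Days unsampled | Share of 28 days | Next scheduled draw |
|---|---|---|---|
| Day 14 | 14 | 50% | Day 29-32 |
| Day 15 | 13 | 46% | Day 29-32 |
| Day 16 | 12 | 43% | Day 29-32 |

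**2. Does another rule close the gap?** I found none.
- Weekly platelet counts are required only after dose escalation (5.1.2.7), dose reduction (5.1.3) or restart (5.1.4).
- In Days 1-28, Table 5-4 keeps a patient with treatment-related platelets of 25-34 on the same dose and requires no repeat count.
- The dose-determining set (Protocol 9.1.3) asks for the required safety evaluations through Day 28. After Amendment 4 the scheduled draws that satisfy this are Days 1 and 15.
- Section 6.1.3 provides for extra evaluations when a patient has unexpected signs or symptoms. DLTs found that way are counted.

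**3. Patients affected.** The Amendment 4 rationale gives 24 Stratum 1 escalation patients, 9 of them at 15 mg BID, so 24 − 9 = 15 at levels 1-4. With at least 3 at each of levels 1, 2 and 4, the number already at 10 mg BID is between 3 and 15 − 9 = 6. The new patients needed to reach about 20 are 20 − 6 = 14 to 20 − 3 = 17. Stratum 2 has 10 − (4 + 2) = 4 expansion places left. The total is 18-21, or fewer if the 01 September 2017 enrolment cap applies first.

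**4. Effect per uncounted DLT on the crude rate.** 1/20 = 5.0 points for the whole 10 mg BID group. Among the new patients alone it is 1/17 = 5.9 to 1/14 = 7.1 points.

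**5. Effect on the model.** For Stratum 1, logit π(d) = log α + β log(d/30), with the Table 9-1 mixture prior (weights 0.9 and 0.1) and 2,000,000 prior draws weighted by the binomial likelihood. The prior check first: P(rate ≥ 33%) at 20, 25 and 30 mg/day came to 0.220, 0.280 and 0.354, against 0.221, 0.281 and 0.355 in Table 9-1.

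The documents do not give DLT counts by dose for Stratum 1, so these are assumed: 0/3 at 10, 15 and 25 mg/day and 2/12 at 30 mg/day. Stratum 2 data are left out. Results at 20 mg/day (10 mg BID):

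| DLTs scored | Posterior mean | P(rate < 16%) | P(rate ≥ 33%) |
|---|---|---|---|
| 6/20 | 0.189 | 0.33 | 0.013 |
| 5/20 | 0.167 | 0.48 | 0.005 |
| 4/20 | 0.146 | 0.64 | 0.002 |

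The assumed counts were then varied over 12 combinations (0-1/3 at 15, 0-1/3 at 25, 1-3/12 at 30 mg/day):
- Each DLT dropped between 6/20 and 4/20 lowers the posterior mean by 2.0-2.3 points.
- Scoring 6/20 as 4/20 lowers the mean by 4.1-4.5 points and raises P(rate < 16%) by 0.16-0.31.
- At 6/20, P(rate ≥ 33%) is 0.006-0.111, below the 25% limit in all 12. At 7/20 it is at most 0.188. At 8/20 it is below 25% in 11 of 12.

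**The case against.** The strongest reply is that the protocol foresees late events. Section 5.1.2.8 says that events after Day 28 meeting every DLT criterion except timing will be considered in escalation decisions and in how many patients to evaluate at a dose. Section 3.1 says later adverse events may be considered when setting cohort size. This stands, and it means a Day 29-32 finding is not ignored. It does not put the event in the DLT count: under 5.1.2.8 only DLTs necessarily enter the model.

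A reader might infer that Day 29-32 results are excluded outright. The text does not go that far. The definition turns on when a toxicity occurs, not when it is first documented, and Table 5-4 governs dosing rather than defining DLTs. An investigator could judge that onset fell inside the window. The gap is a missing attribution rule.

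A reader might also infer that the MSSDs or the choice of 10 mg BID are unsafe. They are not put in doubt. Both MSSDs were declared before Amendment 4, and Protocol 9.1.3 bases them on dose-finding patients only. The rationale for 10 mg BID was dose reductions after cycle 1 and benefit across starting doses. Dosing above the MSSD is barred in expansion, so a higher P(rate < 16%) triggers no escalation.

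Nor does Protocol 1.2.4 show that platelets fall throughout the window. It places most of the median decline in the first 4 weeks, with no split between the first and second fortnight, in patients with baseline counts of at least 100. The number of DLTs arising after Day 15 cannot be estimated from it.

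Finally, the lighter schedule was deliberate: the interim analysis found no new safety signal and visits were cut to reduce burden. That justifies fewer visits, but not placing the end-of-cycle draw one day outside the endpoint's window. SAP 2.3.3 will list graded laboratory values, so the findings will be visible, though not as DLTs.

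**Conclusion.** The point holds as a limited weakness in the primary endpoint for patients starting under Amendment 4. Laboratory DLTs arising between the Day 15 draw and Day 28 may go uncounted unless they cause symptoms, are caught by an unscheduled test, or are dated back by judgment. The possible bias is downward, and its size is unknown and may be zero, because the documents give no within-cycle distribution of onset. It bears on the reported DLT rate and the final posterior table, and on any comparison of 10 mg BID patients before and after the amendment.

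It changes no MSSD. Under the assumed dose-level counts, it also leaves the overdose verdict at 10 mg BID unchanged at 6/20 or fewer DLTs. The figure of 18-21 patients assumes that both expansion targets are filled and that the remaining places were taken up under the new schedule. The change is worth making because it is cheap and the attribution question has to be settled before the final model is reported.

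**What to change.** Keep the DLT definition and make two changes.

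1. **Protocol, for patients still to start.** Move the existing Day 29 (+3) visit, with its hematology and chemistry, to Days 26-28. Confirm adverse events and doses through Day 28 at the next contact if the visit falls on Day 26 or 27. The unsampled end of the window shrinks to 0-2 days with no added visit or draw. The cost is a longer possible wait for the Day 43 (±2) draw: at most 45 − 26 = 19 days instead of 45 − 29 = 16, early in cycle 2.

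2. **SAP 2.3.1 and 2.3.2.** List events that meet a Table 5-3 criterion and are first documented at the Day 29 (+3) visit. Add one model sensitivity run counting them as DLTs. Read it as an upper bound for events still present at that draw, since some may have begun after Day 28. Show 10 mg BID DLTs separately for patients treated before and after Amendment 4. This is one listing, one extra model run and one split table on data already collected. It cannot recover events that resolved before the draw.

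The enrolment cap of 01 September 2017 precedes the SAP release date of 27 Nov 2017, so enrolment has probably closed. In that case only the second change applies.

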**Table 5-3 Criteria for defining dose-limiting toxicities**

Toxicity	Any of the following treatment-related criteria (occurring through Study Day 28)
Hematology	PLT counts $< 25 \times 10^9/L$ * grade 4 neutropenia ( $ANC < 0.5 \times 10^9/L$ )* grade $\geq 3$ febrile neutropenia*
Other AEs	any grade thrombocytopenia requiring PLT transfusion any grade $\geq 2$ hemorrhagic event grade $\geq 2$ serum bilirubin with coincident direct bilirubin $\geq 0.5$ mg/dL grade 3 non-hematologic toxicity for $\geq 7$ consecutive days grade 4 non-hematologic toxicity

\* At the discretion of the Investigator, laboratory values can be confirmed with a second assessment. In this case, only the result of the second assessment will be considered valid and final.

Patients who experience a DLT will have their therapy with INC424 interrupted and will be followed as described in the [Table 5-4](#). After recovery from the toxicity in question, if the Investigator believes that it is in the patient's best interest to resume therapy with INC424, the patient may resume therapy, only after consultation with the Sponsors, according to the guidelines described in the [Section 5.1.3](#) and the [Table 5-4](#).

However, the patient must be permanently discontinued from study medication and withdrawn from the study, if **any** of the following DLTs occur:

- any grade  $\geq 3$  hemorrhagic event
- 2nd episode of grade  $\geq 3$  febrile neutropenia
- grade 3 renal toxicity for  $\geq 7$  consecutive days
- grade 4 renal toxicity

- grade 4 serum bilirubin with direct bilirubin  $\geq 0.5$  mg/dL
- grade 4 non-hematologic toxicity

If, from Study Day 1 through Study Day 28, a patient misses  $> 6$  consecutive doses of treatment or  $> 20\%$  of the planned study drug doses, the patient will not be evaluable for DLTs. The patient can continue in the study, but another patient has to be enrolled at the same dose level and stratum in order to reach the required number of patients in the cohort.

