### **5.1.2.9 Follow-up for dose-limiting toxicities**

Patients whose treatment is discontinued or interrupted due to a DLT, must be followed until resolution or stabilization of the DLT event, whichever comes first, as described in [Section 6.1.4](#).

In the case of PLT transfusion that is considered unrelated to the treatment with INC424 (e.g., car accident causing bleeding and subsequent PLT transfusion despite grade  $\leq 3$  thrombocytopenia), then no measures should be taken, other than those related to the management of the event ([Table 5-4](#)). If the event for which the PLT transfusion was given is considered related to the treatment with INC424, then both the PLT toxicity-handling guidelines and the hemorrhagic event-handling guidelines should be taken into account.

In case of a hemorrhagic event of any grade (CTCAE grade 1 included) the Investigator is advised to perform coagulation tests and albumin assessment.

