### **5.1.3 Dose modification and dose delay**

All dose modifications should be based on the worst preceding toxicity. Patients may be allowed dose reductions to 5 mg qd (dose level (-1)). Dose reductions more than one level at a time will not be allowed, except for thrombocytopenia, in which case different rules for dose reductions apply ([Table 5-4](#)). Note that the maximum allowed doses are quoted in the part of [Table 5-4](#) where guidelines for dose reduction due to thrombocytopenia are provided; lower doses may be used at investigator discretion. It is recommended that patients who are dose reduced for thrombocytopenia have more frequent hematology assessments. PLT counts must be obtained at least weekly for 4 weeks, and then at least every second week for the next 4 weeks. Thereafter, they may resume monthly evaluations.

Recovery of platelet counts will allow dose increases according to the guidelines in [Table 5-5](#). Note that once a dose is re-escalated, any subsequent declines in platelet count will require that [Table 5-4](#) be used to determine the new lower dose, or dose interruption.

Dose level (-1) is the lowest acceptable dosing level for a patient participating in the study. If a patient cannot tolerate dose level (-1), then he/she must be discontinued from study medication and withdrawn from the study (see [Table 5-2](#) for dose level definitions).

Dose modifications for toxicities occurring during the DLT-definition period (Study Day 1 through Study Day 28), and considered as treatment-related, will **not** be allowed until the toxicity qualifies as a DLT. After a toxicity event has been characterized as a DLT, a patient can resume therapy with a reduced INC424 dose according to the guidelines provided in the [Section 5.1.2.7](#). Dose modification recommendations after Study Day 28 are described in the [Table 5-4](#).

Any dose modifications must be recorded on the Dosage Administration Record eCRF.

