#### **5.1.4 Treatment interruption and treatment discontinuation**

Patients may continue treatment with INC424 for the duration of the study or until they experience unacceptable toxicity that precludes any further treatment, disease progression, and/or at the discretion of the Investigator. Patients will be discontinued from the study if they withdraw consent, or if the treating physician judges that further therapy with INC424 is no longer in the patient's best interest.

Criteria for interruption and re-initiation of INC424 treatment are summarized in the [Table 5-4](#). A patient must discontinue treatment with INC424 if, after treatment is resumed at a lower dose, the same toxicity recurs with the same or worse severity. If a patient requires a dose delay of > 28 days, then the patient must be discontinued from the study. Patients who discontinue from the study for a treatment-related adverse event or a treatment-related abnormal laboratory value must be followed as described in [Section 6.1.4](#).

Grading of toxicity will be according to CTCAE Version 4.03.

Doses may be restarted and subsequently increased, according to the [Table 5-6](#), provided that platelet counts recover to  $\geq 35 \times 10^9/L$  and ANC counts recover to  $\geq 0.75 \times 10^9/L$  and there is no other toxicity that precludes dosing of the patient. Note that once a dose has been restarted, subsequent declines in platelet or ANC count will require that [Table 5-4](#) be used to determine the new lower dose or dose interruption. It is required that patients who have restarted dosing have more frequent hematology assessments. PLT and ANC counts must be obtained at least weekly for 4 weeks, and then at least every second week for the next 4 weeks. Thereafter, they may resume monthly evaluations (exception: for grade 4 thrombocytopenia or neutropenia events please refer to [Section 5.1.2.9.1](#)).

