$\geq 75 \times 10^9 / L$ $50 - 74 \times 10^9 / L$ $35 - 49 \times 10^9 / L$ $25 - 34 \times 10^9 / L$ $< 25 \times 10^9 / L$	Continue at same dose level Continue at same dose level Continue at same dose level Continue at same dose level * Hold dosing  * qualifies as a DLT. If resolved to ≤ grade 2, resume therapy according to the rules of Table 5-6 .	Dose at the Time of the Platelet Decline 
 
 5 mg qd	5 mg b.i.d.	5 mg q.AM / 10 mg q.PM	10 mg b.i.d.	10 mg q.AM / 15 mg q.PM	15 mg b.i.d.	
 
 New Maximum Dose That Must be Instituted 
 
 Continue at same dose level	10 mg b.i.d.†	10mg b.i.d.†	
 
 Continue at same dose level	Continue at same dose level‡	
 
 Continue at same dose	5 mg b.i.d.	5 mg b.i.d.	5 mg b.i.d.	5 mg b.i.d.	
 
 5 mg qd	
 
 Discontinue	Hold dosing	
 
 †Patients from stratum 1 ‡Patients from stratum 2						5 mg qd	5 mg b.i.d.	5 mg q.AM / 10 mg q.PM	10 mg b.i.d.	10 mg q.AM / 15 mg q.PM	15 mg b.i.d.	Continue at same dose level			10 mg b.i.d.†	10mg b.i.d.†	Continue at same dose level			Continue at same dose level‡			Continue at same dose		5 mg b.i.d.	5 mg b.i.d.	5 mg b.i.d.	5 mg b.i.d.	5 mg qd	Discontinue	Hold dosing									
5 mg qd	5 mg b.i.d.	5 mg q.AM / 10 mg q.PM	10 mg b.i.d.	10 mg q.AM / 15 mg q.PM	15 mg b.i.d.																																					
Continue at same dose level			10 mg b.i.d.†	10mg b.i.d.†																																						
Continue at same dose level			Continue at same dose level‡																																							
Continue at same dose		5 mg b.i.d.	5 mg b.i.d.	5 mg b.i.d.	5 mg b.i.d.																																					
5 mg qd	5 mg qd	5 mg qd	5 mg qd	5 mg qd	5 mg qd																																					
Discontinue	Hold dosing																																									
In cases of grade 4 thrombocytopenia, follow-up rules according to Section 5.1.2.9.1 . For dose escalation or dose restart guidelines, see Table 5-5 and Table 5-6 .																																										

**Table 5-5 Dose escalation guidelines and allowed maximum doses for patients who have previously decreased dosing for thrombocytopenia**

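### Related thrombocytopenia needing platelet transfusion on Days 1-28 is a DLT that calls for interruption, but Table 5-4 has no row for it and says to continue at every count of 25 or more, with no stated precedence

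*Protocol*

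**What the plan says.** All references are to the protocol; counts are x 10^9/L.

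- **DLT definition.** Section 3.1 and Table 5-3 both list treatment-related "any grade thrombocytopenia requiring PLT transfusion" through Study Day 28 as a DLT. No count is attached.
- **Action after a DLT.** Section 5.1.2.8, under Table 5-3, states: "Patients who experience a DLT will have their therapy with INC424 interrupted". It refers to Table 5-4 for follow-up and allows resumption only after consultation with the Sponsors.
- **Dose table.** The Table 5-4 thrombocytopenia block has five count bands: 75 or more, 50-74, 35-49, 25-34 and below 25. For related toxicity on Days 1-28 the entries read, in that order: "Continue at same dose level Continue at same dose level Continue at same dose level Continue at same dose level * Hold dosing". The DLT mark is on the last band only. The table's title describes its content as "Recommended dose modifications".
- **Related transfusion.** Section 5.1.2.9 says that, when the event behind the transfusion is related to INC424, "then both the PLT toxicity-handling guidelines and the hemorrhagic event-handling guidelines should be taken into account".
- **Resumption.** Section 5.1.3 bars modification for related toxicity in the DLT window until the toxicity qualifies as a DLT. After that, "a patient can resume therapy with a reduced INC424 dose according to the guidelines provided in the" section on intra-patient escalation (5.1.2.7). It also bases modifications on the worst preceding toxicity. Section 5.1.4 adds "Doses may be restarted and subsequently increased, according to the" restart table (Table 5-6), once platelets reach 35 and ANC reaches 0.75. After a restart, "PLT and ANC counts must be obtained at least weekly for 4 weeks".

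**The concern.** For one of the listed DLTs, the text and the dose table give opposite instructions. A site that looks up the platelet count in Table 5-4 is told to keep the full dose in a patient who has just had a DLT from the drug's known toxicity. A site that follows Section 5.1.2.8 stops the drug. At stake is how an individual patient is dosed and how closely platelets are then watched. The fixed weekly count schedules follow a dose reduction (5.1.3) or a restart (5.1.4), and weekly follow-up follows an interruption for an adverse event (6.1.4). An unchanged dose triggers none of them.

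**Working it through.** The plan gives no figure to reproduce. The check is a comparison of rules, followed by simple dose arithmetic.

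**1. Is the gap specific to this criterion?** Table 5-3 has eight criteria. Seven have an entry marked as a DLT in Table 5-4: platelets below 25, grade 4 neutropenia, febrile neutropenia, hemorrhage of grade 2 or more, bilirubin, prolonged grade 3 non-hematologic toxicity and grade 4 non-hematologic toxicity. Platelet transfusion is the only one without.

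**2. What do the rules give for a related transfusion on Days 1-28?**

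- Count below 25: Section 5.1.2.8 says interrupt and Table 5-4 says hold. They agree.
- Count 25 or more with a related bleed of grade 2 or higher: the hemorrhage rows require a hold or discontinuation. They agree with Section 5.1.2.8.
- Count 25 or more with no bleed, or a related grade 1 bleed: Section 5.1.2.8 says interrupt. The thrombocytopenia row and the grade 1 hemorrhage row both leave the dose unchanged, so applying both guidelines, as Section 5.1.2.9 asks, does not produce a hold.

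Table 5-3 files the event under other AEs. The corresponding Table 5-4 rows for related toxicity also leave the dose unchanged for grades 1 and 2, and for grade 3 lasting under 7 days. No section ranks Section 5.1.2.8 against Table 5-4.

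**3. Dose difference.** Inputs: 10 mg b.i.d., the starting dose for new patients in both strata under Amendment 4; a count of 25-34; Table 5-4; Table 5-6.

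- Table 5-4, Days 1-28: 2 x 10 = 20 mg/day.
- Section 5.1.2.8: 0 mg/day.
- Restart, if Table 5-6 is applied: hold below 35. At 35-49, 5 mg/day, which is 1 - 5/20 = 75% lower. At 50 or more, 10 mg/day, which is 1 - 10/20 = 50% lower.
- Table 5-4 from Day 29, same count, without any transfusion: maximum 5 mg/day. The Day 1-28 entry therefore allows 20/5 = 4 times that dose.

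**4. Duration.** Table 6-1 schedules hematology on Days 1, 15 and 29, and Section 6.1.3 requires no laboratory-only visits. For an event at the Day 15 visit, 29 - 15 = 14 days; 14 x 2 = 28 doses; 28 x 10 = 280 mg before the Day 29 rules apply.

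**5. Does interrupting settle the restart?** Only in part. The Table 5-6 title is limited to grade 4 holds. Its platelet ceiling is tied to the dose at which the count first fell below 25, which a patient transfused at 25 or more may never have had. The platelet row for counts of 50 or more allows a return to that dose, whereas the note under the table sets the limit 5 mg qd below it. Section 5.1.3 points to the intra-patient escalation section for resumption.

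**The case against.** The strongest reply is that the protocol already favours interruption. Section 5.1.2.8 is mandatory and specific to DLTs, and it cites Table 5-4 for follow-up and resumption, not for whether to interrupt. Table 5-4 is titled as recommendations. Section 5.1.3 bars modification only until the event becomes a DLT, then speaks of a reduced dose, and it bases changes on the worst preceding toxicity. On that reading the unchanged-dose entries describe the patient before the event qualifies as a DLT. Section 5.1.2.9 asks that both guidelines be considered; it does not order the dose to continue.

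This stands as the better reading. It remains an inference from several sections, while the table used at the bedside says the opposite.

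A reader might also infer that the lack of a bar on returning to the transfusion dose is itself a defect. The documents do not support that. The Amendment 3 rationale deliberately allows, at the physician's discretion, a return to the dose where platelets first declined. Other safeguards exist: Sponsor consultation, a reduced dose on resumption, and Table 5-6 increases of 5 mg qd no faster than one per 28-day cycle. The ceiling is the sponsor's choice. What needs repair is that the Table 5-6 row and note disagree and that neither defines a ceiling for this hold.

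The pointer to 5.1.2.7 looks like a renumbering slip, since Section 9.4.1 also cites 5.1.2.7 for the DLT definition. The row/note mismatch affects every grade 4 platelet hold. Both are separate from the main conflict.

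**Conclusion.** The conflict is real but narrow: a related platelet transfusion on Days 1-28, at a count of 25 or more, without a related bleed of grade 2 or higher. Interruption is the better reading, but no order of precedence is stated. In the worked case the two instructions differ by 20 mg/day against 0, for about 14 days (28 doses, 280 mg). This assumes the event falls on Day 15, no unscheduled count prompts a change, and the site follows the table. A careful site would test sooner, and Section 7.1.1 asks for adverse events to be followed more often than each visit if necessary, but it sets no platelet schedule.

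Three stronger readings are not supported:

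- That dose finding is compromised. The DLT definition is clear in Table 5-3, Section 5.1.2.8 feeds DLTs to the BLRM, and SAP Sections 2.1.1 and 2.3.2 follow it. Classification and the MSSD are unaffected.
- That a probability of occurrence can be given. The documents contain no rate for this event.
- That full dosing could run to Day 32 by using the Day 29 visit window. From Day 29 Table 5-4 caps a count of 25-34 at 5 mg/day.

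It should be fixed because a written entry would keep the full dose after a DLT and the correction is cheap.

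**What to change.** Add a row or footnote to the thrombocytopenia block of Table 5-4: related thrombocytopenia requiring platelet transfusion at any count, Days 1-28, is a DLT; hold dosing; restart at a reduced dose per Table 5-6 after Sponsor consultation. Extend the Table 5-6 title to cover this hold.

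Separately, make the Table 5-6 platelet row and its note agree. The sponsor should choose the ceiling in line with the Amendment 3 rationale and state how it applies to this hold. Correct the pointer to 5.1.2.7 in Section 5.1.3.

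The cost is one table row or footnote, one title, one reconciled ceiling and one cross-reference, with a letter to sites. No new visits or patients are needed.
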